Visit	Assessment	Limits for allowance of out-of-window collection
Visit 5/Week 4	PK	up to 3 weeks early or late (\pm 21 days) (Section 10.1.3)
	BMI	up to 3 weeks late (+ 21 days)
Visit 7/Week 8 or ET	PK	up to 1 week late (+ 7 days) (Section 10.1.3)
	Clinical chemistry, hematology, urine drug screen	up to 1 week late (+ 7 days)*
	Physical examination, BMI, vital signs, ECG, urinalysis, pregnancy test	up to 1 week late (+ 7 days)*
Visit 8/Week 9	Vital signs	up to 1 week late (+ 7 days)*

Abbreviations: BMI = body mass index; ECG = electrocardiogram; ET = End of Treatment; PK = pharmacokinetic. Note, if subjects cannot do the assessments within these timeframes, it will be noted as missing assessment(s) for that visit. NOTE: PK assessments outside the above visit windows should not be done at all.

* For purposes of including as safety endpoints, these assessments will be included in the safety analysis if collected up to 1 week late. Any safety data collected 8 days to 42 days late will be considered missing for analysis purposes. The 6-week window is allowed to capture any follow-up safety data on the participant and will be noted in the final study report (see also [Section 11.6](#)).

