3.2 SCHEDULE OF ASSESSMENTS

Period	Screening Period		Double-blind Down Taper Period	Follow-up					
Visit	1	2	3	4	5	6	7/ET ^a	8 _p	Telephone Contact
Day/Week	Day -21 to -1	Baseline Day 1	Week 1°	Week 2°	Week 4 ^c	Week 6 ^c	Week 8/ET ^c	Week 9°	Week 10 ^c
Subject Informed Consent/Assent	X								
Parent Informed Consent	X								
Inclusion/Exclusion Criteria	X	X							
Demographics	X								
Medical History	X								
Psychiatric History	X								
Medication History	X								
MINI Kid	X								
Physical Examination	X						X		
Body Mass Index (BMI)	X				X		X		
Randomization		X							
Vital Signs ^d	X	X	X	X	X	X	X	X	
Electrocardiogram (ECG)	X						X		
Urine Drug Screen	X						X		
Screen for HBsAg, HCVAb, HIV	X								
Clinical Chemistry including Thyroid	Xe						X		
Hematology	X						X		
Urinalysis	X						X		
Pregnancy Test ^f	X	X					X		
C-SSRS	X	X	X	X	X	X	X	X	
CGAS	X	X	X	X	X	X	X		
PARS	X	X		X			X		
CGI-S	X	X		X			X		
Global COVID-19 Impact Assessment ⁸	X	X	X	X	X	X	X		

Page 12 of 53

Evaluate for Dose Escalation ^h				X	X				
PK Blood Samples ⁱ					X		X		
Dispense Study Drug		\mathbf{X}^{j}	X	X	X	X	X		
Study Drug Accountability			X	X	X	X	X	X	
Adverse Events		4							
Concomitant Medications	4								

Abbreviations: BMI = body mass index; CGAS = Children's Global Assessment Scale; CGI-S = Clinical Global Assessment of Severity; COVID-19 = coronavirus disease 2019; C-SSRS = Columbia-Suicide Severity Rating Scale; ECG = electrocardiogram; ET = End of Treatment; HBsAg = hepatitis B surface antigen; HCVAb = hepatitis C virus antibody; HIV = human immunodeficiency virus; MINI Kid = Mini-International Neuropsychiatric Interview for Children and Adolescents; PARS = Pediatric Anxiety Rating Scale; PK = pharmacokinetic.

^a End of Treatment or Early Withdrawal.

^b If a site becomes aware of any adverse events after study completion (occurring outside of a defined study visit, including any contact up to 30 days after study completion), all adverse events reported by the patient or patient representative or observed or otherwise identified by the investigator or other study personnel must be documented.

^c Visit window ± 3 days. Refer to Section 8.2.2.1, Table 1 of the protocol for visit windows for safety assessments (physical examination, BMI, vital signs, ECG, urine drug screen, clinical chemistry including thyroid, hematology, urinalysis, pregnancy test) and/or PK assessments missed due to remote visits.

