9.2.8 Analysis of COVID-19 impact assessment score

The global COVID-19 impact assessment will be used to evaluate the impact of the coronavirus disease pandemic on the severity of the subject's GAD during the last 1 week. The rating will include scores from 0 (not applicable, subject not enrolled in the trial during the pandemic) to 7 (extreme impact). Raters will also evaluate whether the impact was an improvement or worsening of the subject's GAD.

Subjects with scores from 4 (moderate impact) to 7 (extreme impact) at any visit other than the Screening Visit will be considered to have been significantly impacted, regardless of the direction of impact.

Number and percentage of subjects with each score on the global COVID-19 impact assessment will be summarized descriptively at each visit by treatment group for the mITT population, including subjects that were significantly impacted. For each score from 2 to 7, the number and percentage of subjects who improved or worsened will also be summarized.

Page 29 of 53

Page 30 of 53

10.0 SAFETY ANALYSES

The safety analysis will be performed for the double-blind acute treatment period and the double-blind down-taper period separately, using the Safety Population unless stated otherwise.

The safety parameters include adverse events (AEs), clinical laboratory parameters, vital signs, electrocardiographic (ECG) parameters, and suicide risk assessment using the Columbia-Suicide Severity Rating Scale (C-SSRS). For each safety parameter, the last non-missing safety assessment before the first dose of double-blind investigational product will be used as baseline. Continuous variables will be summarized by number of subjects and mean, SD, median, minimum, and maximum values. Categorical variables will be summarized by number and percentage of subjects.

Safety data collected outside of planned visit windows but within allowance limits (up to 1 week late for Visits 7 and 8) will be included in the summary tables. Safety data collected outside of planned visit windows and outside of the allowance limits (>1 week to 6 weeks late for Visits 7 and 8) will be listed, but will not be included in the summary tables. Subgroup analyses may be performed to assess the impact of COVID-19 on the safety analyses; details are listed in each safety section.

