16.1 VISIT TIME WINDOWS

Table 16.1–1 and Table 16.1–2 present the visits assigned for efficacy and safety analyses and the corresponding ranges of treatment days (window) during which an actual visit may occur.

Table 16.1–1. Visit Time Windows

Derived Visit	Scheduled Visit (Day) ^a	Window
Baseline ^b	Week 0 (Day 1)	Days ≤ 1
Week 1	Week 1 (Day 8)	Days [2, 11]
Week 2	Week 2 (Day 15)	Days [12, 21]
Week 4	Week 4 (Day 29)	Days [22, 35]
Week 6	Week 6 (Day 43)	Days [36, 49]
Week 8	Week 8 (Day 57)	$Days \geq 50 \ days \ and \ within \ double-blind \ acute \\ treatment \ period$
End of double-blind acute treatment period ^c	Final or termination visit du	ring the double-blind acute treatment period

a Relative to the date of the first dose of double-blind investigational product. Day 1 = the date of the first dose of double-blind investigational product.

Table 16.1–2. Visit Time Windows for the Double-Blind Down-Taper Period

Derived Visit	Scheduled Visit	Window
Week 9/Down-Taper Period	Week 9	Within the double-blind down-taper period (from 1 day after the end of double-blind acute treatment period to the end of the double-blind down-taper period)
End of double-blind down-taper period ^a	Final or termination vi	sit during the double-blind down-taper period

a Presented in analysis tables for safety parameters collected during the double-blind down-taper period. If any assessments are repeated at the end-of-double-blind-down-taper-period visit or during any visit window, the algorithm in Section 16.3 will be used to determine which values are used in the analysis.

b The window for selecting baseline values is from 30 days before the first dose of double-blind investigational product to Day 1.

c Presented in analysis tables for safety parameters, including but not limited to electrocardiograms, clinical laboratory values, vital signs, and C-SSRS. If repeated assessments occur at the end of double-blind acute treatment period visit or during any visit window, the algorithm in Section 16.3 will be used to determine which values are used in the analysis.

Page 43 of 53

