16.3 REPEATED OR UNSCHEDULED ASSESSMENTS OF SAFETY PARAMETERS

If a subject has repeated assessments before the date of first dose of double-blind investigational product, the results from the final nonmissing assessment made before the date of the first dose of double-blind investigational product will be used as baseline. If end-of-double-blind-treatment period assessments are repeated or if unscheduled visits occur, the last nonmissing post-baseline assessment during the double-blind acute treatment period will be used as the end-of-double-blind-acute-treatment-period assessment for generating summary statistics. Likewise, if end of double-blind down-taper period assessment during the double-blind down-taper period will be used as the end-of-double-blind-down-taper-period assessment for generating summary statistics.

Similarly, if a subject has repeated assessments within a given visit window, the last non-missing post-baseline assessment during the window will be used as the assessment for that visit window when generating summary statistics.

However, all post-baseline assessments will be used to determine PCS values for laboratory parameters, vital signs and ECG parameters, and to determine most severe suicidal ideation and most severe suicidal behavior from C-SSRS. All assessments will be presented in the data listings.

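### SAP 16.1 and 16.3 have no rule for the late Visit 7 safety tests that SAP 10.0 and protocol Table 1 keep; followed literally, they move a subject's only scheduled post-baseline ECG or laboratory value out of the Week 8 and shift tables

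*SAP*

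**What the plan says.** Protocol 8.2.2.1, Table 1, sets limits for tests missed because of a remote visit. For Visit 7/Week 8 or ET, the limit is 7 days late for laboratory tests, ECG, vital signs and the other listed safety tests. For the rows marked with an asterisk (the Visit 7 safety tests and Visit 8 vital signs), the footnote says "these assessments will be included in the safety analysis if collected up to 1 week late" and then "Any safety data collected 8 days to 42 days late will be considered missing for analysis purposes". The table note adds that "if subjects cannot do the assessments within these timeframes, it will be noted as missing assessment(s) for that visit".

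The SAP adopts this in two places. Footnote c to the schedule in SAP 3.2 says "Refer to Section 8.2.2.1, Table 1 of the protocol for visit windows for safety assessments". SAP 10.0 says that data outside the planned windows but "within allowance limits (up to 1 week late for Visits 7 and 8) will be included in the summary tables"; later data are listed only. The same section has the acute and down-taper periods analysed separately.

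Readings are assigned to visits in SAP 16. In Table 16.1-1, Week 8 is Day 50 or later, provided the reading lies inside the acute period; the end-of-acute row takes the final or termination visit of that period. In Table 16.1-2, the Week 9/Down-Taper row runs "from 1 day after the end of double-blind acute treatment period to the end of the double-blind down-taper period". Where assessments are repeated or unscheduled, 16.3 says "the last nonmissing post-baseline assessment during the double-blind acute treatment period will be used" for the end-of-acute summary. Section 16.3 then makes PCS values an exception, for which every post-baseline assessment is used. Neither 16.1 nor 16.3 mentions the late allowance, and SAP 17.0 declares no change on this point.

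**The concern.** A test inside the Table 1 limit is not missing for Visit 7, so the protocol treats it as Visit 7 data. The SAP's assignment rules, taken as written, treat the same test as down-taper data. Two competent programmers could therefore build different Week 8 tables from the same SAP.

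The consequence is sharpest for ECG and laboratory tests. Their only scheduled post-baseline time point is Week 8/ET, and the shift tables in SAP 10.2 and 10.4 run from baseline to the end of acute treatment. No ECG or laboratory test is scheduled at Visit 8, so a value moved to the taper row sits where no such test was planned. Safety is part of the primary objective, so the basis of these tables should be fixed in writing before unblinding.

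The PCS rule raises a second question: whether a reading taken more than a week late can enter a PCS incidence table.

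**Working it through.** No stated figure needs reproducing. The check is study-day arithmetic plus a comparison of the rules.

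**Inputs.** Study day = visit date − first-dose date + 1 (SAP 16.1). Visit 7 is 8 weeks ± 3 days after baseline and Visit 8 is 9 weeks ± 3 days (protocol 9.2.5 and 9.3.1). The Table 1 allowance is +7 days. Three assumptions are needed:
- Lateness is counted from the actual Visit 7 date. Protocol 8.2.2.1 counts its 6-week limit from that date.
- The taper lasts 7 days.
- The acute period ends on the Visit 7 date, or 1 or 3 days later. The SAP does not date its end. Exposure is counted through the Week 8/ET visit (SAP 8.1) and taper drug is dispensed there (protocol 9.2.5), so the Visit 7 date is the natural first choice.

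**Days.** Visit 7: 8 × 7 + 1 = Day 57, window Days 54–60. Visit 8: 9 × 7 + 1 = Day 64, window Days 61–67.

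**Mapping of the 7 allowed late days** (Week 8 / Down-Taper):

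| Visit 7 on | Late days | Acute end = Visit 7 | Acute end +1 | Acute end +3 | Late days inside the Visit 8 window |
|---|---|---|---|---|---|
| Day 54 | 55–61 | 0 / 7 | 1 / 6 | 3 / 4 | 1 |
| Day 57 | 58–64 | 0 / 7 | 1 / 6 | 3 / 4 | 4 |
| Day 60 | 61–67 | 0 / 7 | 1 / 6 | 3 / 4 | 7 |

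In general, with the acute period ending k days after Visit 7, 7 − k late days go to the taper row. Every late day is past Day 50, so the period condition alone removes the reading from Week 8. With the allowance written into 16.1 and 16.3, all 7 days would map to Week 8.

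**What a late-tested subject loses.** ECG and laboratory tests: 1 of 1 scheduled acute post-baseline time points. Vital signs: 1 of 5 (Weeks 1, 2, 4, 6, 8).

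**Displacement.** A late Visit 7 vital sign and the Visit 8 vital sign can both fall in the taper window. SAP 16.1 and 16.3 then use the last non-missing one. With Visit 7 on Day 57, a reading on Day 60 would give way to the Visit 8 reading on Day 64 and leave the by-visit summaries.

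**PCS.** Take a Visit 7 ECG done 10 days late. Under SAP 10.0 it is listed but not summarised, and under protocol Table 1 it is missing for analysis. Under the PCS sentence in 16.3 it is a post-baseline assessment and counts. The rules give opposite answers for that reading.

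**The case against.** The best reply is that SAP 10.0 already governs. It is the specific rule, it names Visits 7 and 8, and 16.1 is general windowing. Since ECG and laboratory tests have no taper time point and SAP 17.0 declares no further change from the protocol, the sensible reading is Week 8. That is probably what was intended, and a reader who infers that the SAP drops the allowance altogether goes too far. But 10.0 says only that the data enter the summary tables. It names no derived visit, and it splits the analysis by period. Filing the reading under Week 9 arguably satisfies 10.0 and still empties the Week 8 and shift entries.

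Other parts of the reply stand. The end of the acute period is undated, so the effect is a range. SAP 3.0 places table specifications in a separate document, not seen here, which may contain the mapping. On PCS, the 16.3 sentence follows a rule on repeats and may have been meant only to contrast with taking the last value; it does not say so.

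A reader might also extend the point to Visit 5 BMI, which Table 1 allows up to 21 days late while the Week 4 window closes on Day 35. The documents do not support this. That row has no asterisk, protocol 11.6 and SAP 10.0 limit the analysis allowance to Visits 7 and 8, and nothing says a late BMI is to be analysed as Week 4.

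**Conclusion.** The conflict is real. Protocol Table 1 and SAP 10.0 keep Visit 7 safety tests done up to 7 days late. Followed literally, SAP 16.1 and 16.3 assign 7 − k of those 7 days to Week 9/Down-Taper: all 7 if the acute period ends on the Visit 7 date. The subject then has no Week 8 change or shift entry for ECG and laboratory tests. The PCS rule in 16.3 separately conflicts with the exclusion of data more than a week late.

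The reach is narrow: descriptive safety tables, for subjects tested late after remote visits. The documents do not say how many there are, so no count is given. A reader might infer that safety results are biased or that the values vanish; neither follows. No direction of bias can be derived, and the readings remain in the listings and count towards PCS under 16.3. Efficacy, treatment-emergent adverse events and the C-SSRS are unaffected. The conclusion rests on the SAP text as written and on counting lateness from the Visit 7 date.

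**What to change.** Reconcile SAP 16.1 and 16.3 with SAP 10.0 and protocol Table 1:

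1. State that Visit 7/ET safety tests covered by Table 1 and done up to 7 days after the Visit 7 date are assigned to Week 8/end of acute treatment. A vital-sign reading that fits both Visit 7 and Visit 8 goes by its eCRF visit label and is counted once. If the sponsor prefers the taper assignment, declare it as a departure in SAP 17.0.
2. State in 16.3 that PCS summaries exclude Visit 7 and 8 data beyond the 10.0 allowance, which stay in the listings.

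The cost is a few sentences and one visit-mapping rule in programming. Dosing, visits and efficacy windows do not change. The downside is that some Week 8 values will have been taken during the taper, when exposure may already be reduced (protocol 8.4.1). Flagging those readings, with an optional supplementary table that excludes them, would show whether this matters; neither document requires that addition.

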10.1 ADVERSE EVENTS

Adverse events will be coded by SOC and PT using the MedDRA version 22.0 or newer.

An AE (classified by PT) that occurs during the double-blind acute treatment period, during the down-taper period, or within 30 days after the date of the last dose of double-blind investigational product will be considered a treatment-emergent adverse event (TEAE) if it was not present before the date of the first dose of double-blind investigational product, or was present before the date of the first dose of double-blind investigational product and increased in severity during the double-blind acute treatment period or during the down-taper period, respectively.

If more than 1 AE was reported before the date of the first dose of double-blind investigational product and coded to the same preferred term, the AE with the greatest severity will be used as the benchmark for comparison with the AEs occurring during the double-blind acute treatment period or during the down-taper period that were also coded to that preferred term. An AE that occurs more than 30 days after the date of the last dose of double-blind investigational product in the study will not be counted as a TEAE but will be included in the listings.

Page 31 of 53

An AE occurring during the down-taper period or safety follow-up period will be considered a newly emergent AE (NEAE) if it is not present before the start of the down-taper period or was present before the start of the down-taper period but increased in severity during the down-taper period. All NEAEs will be summarized by SOC, PT, and treatment group.

The number and percentage of subjects in each treatment group reporting TEAEs during the double-blind acute treatment period will be tabulated by SOC and PT; by SOC, PT, and severity; and by SOC, PT, and causal relationship to the investigational product. If more than one AE is coded to the same PT for the same subject, the subject will be counted only once for that PT using the most severe and most related occurrence for the summarization by severity and by causal relationship to the investigational product, respectively. Study-treatment-related TEAEs are defined as TEAEs with relationship to treatment categorized as Possible, Probable, Very, Like/Certain or missing.

The distribution of TEAEs by severity and causal relationship to the investigational product will be summarized by treatment group. The incidence of common ($\geq 2\%$ of subjects in any treatment group) TEAEs during the double-blind acute treatment period will be summarized by PT and treatment group.

A serious adverse event (SAE) that occurred between the date of the first dose of double-blind investigational product and 30 days after the date of the last dose of double-blind investigational product in the study, inclusive, will be considered an on-therapy SAE. The incidence of SAEs and AEs leading to premature discontinuation of the study will also be summarized by study period (separately for double-blind acute treatment period and double-blind down taper period), SOC, PT, and treatment group.

The above summaries will be sorted by decreasing frequency of SOC and by the decreasing frequency of PT within SOC for the escitalopram treatment group. If incidence for more than 1 term is identical, they will then be sorted alphabetically. In addition, the above summaries will be presented as all AEs, AEs that are associated with the COVID-19 pandemic (as determined by the investigator), and AEs that are not associated with the COVID-19 pandemic. AEs associated with the COVID-19 pandemic will be listed separately.

Listings will be presented for subjects with SAEs, subjects with AEs leading to premature discontinuation, and subjects who died for the Screened Population. All subjects with SAEs, including those reported during the screening period or more than 30 days after the date of the last dose of the double-blind investigational product, and subjects discontinuing due to AEs before the start of double-blind investigational product will be included in these listings

Page 32 of 53

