Within 24 hours of learning of any AE that meets one of the criteria for an SAE, the study center personnel must report the event to Global Drug Safety on the SAE Form for Clinical Trials. The medical director may also be notified by telephone, however, notification of the medical director by telephone does not substitute for reporting of the event to the sponsor by email/fax of the SAE form for Clinical Trials within the required time period.

If, during follow-up, any nonserious AE worsens and eventually meets the criteria for an SAE, that AE should be recorded as a new SAE.

The study center must transmit the SAE Form for Clinical Trials to the SAE email address or fax number shown below. Even if an initial report is made by telephone, the SAE Form for Clinical Trials completed with all available details must still be faxed or emailed within 24 hours of knowledge of the event at the study center.

Supplemental information should be submitted as soon as available and may include laboratory results, radiology reports, progress notes, hospital admission and emergency

CONFIDENTIAL

room notes, holding and observation notes, discharge summaries, autopsy reports, and death certificates.

The investigator is expected to take all therapeutic measures necessary for resolution of the SAE. Any medications or procedures necessary for treatment of the SAE must be recorded on the appropriate pages of the subject's eCRF. All SAEs are to be followed by the study staff until resolution or until the SAE is deemed stable. *The sponsor may contact the study center to solicit additional information or follow up on the event.*

Fax or email the SAE Form for Clinical Trials to the following SAE fax number/email address:

[contact] (back-up [contact])
Email: [contact]

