11.6.1.1 Adverse Events

AEs will be coded to an SOC and PT using the latest available version of MedDRA. An AE (classified by PT) not present before the date of the first dose of the double-blind treatment period or during the double-blind down taper period or that was present before the first dose but increased in severity or seriousness will be considered a TEAE. An AE that starts more than 30 days after the date of the last dose of double-blind investigational product will not be counted as a TEAE.

An AE that starts during the double-blind down taper period or that increases in severity or seriousness during the double-blind down taper period will be considered a newly emergent AE (NEAE). The NEAEs during the double-blind down taper period will be summarized by SOC, PT, and treatment group for all subjects who enter the double-blind down taper period.

CONFIDENTIAL

The number and percentage of subjects reporting TEAEs in each treatment group will be tabulated by SOC and PT; by SOC, PT, and severity; and by SOC, PT, and causal relationship to the investigational product. If more than one AE is coded to the same PT for the same subject, the subject will be counted only once for that PT using the most severe and most related occurrence for the summarization by severity and by causal relationship to the investigational product, respectively.

The distribution of TEAEs by severity and causal relationship to the investigational product will be summarized by treatment group. The incidence of common ($\geq 2\%$ of subjects in any treatment group) TEAEs during the double-blind treatment period will be summarized by PT and treatment group.

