16.9 CHARACTER VALUES OF CLINICAL LABORATORY PARAMETERS

If the reported value of a clinical laboratory parameter cannot be used in a statistical summary table because, for example, a character string is reported for a parameter of the numeric type, a coded value must be appropriately determined for use in the statistical analyses. The actual values, as reported in the database will be presented in the data listings.

Table 16.9–1 shows examples of how some possible laboratory results should be coded for analysis.

Page 49 of 53

Table 16.9–1. Examples of Coding Special Character Values for Clinical Laboratory Parameters

Laboratory Test, SI Unit	Possible Laboratory Results	Coded Value for Analysis
CHEMISTRY		 
ALT, U/L	< 5	5
AST, U/L	< 5	5
Bilirubin, total, μmol/L	< 2	2
URINALYSIS		
	< 2.775, Negative	0
	[2.775, 5.55)	1+
C1	[5.55, 13.875)	2+
Glucose, mmol/L	[13.875, 27.75)	3+
	[27.75, 55.5)	4+
	≥ 55.5	5+
141/T	$> 0.444, \ge 0.444, >0$, Trace	Positive
ketones, mmol/L	≤ 0, Negative	Negative
pH	> 8.0, ≥ 8.0	8.0
	≥ 8.5	8.5
	< 0, Negative	Negative
	[0, 0.15), Trace	0
Dustain a/I	[0.15, 0.3)	1+
Protein, g/L	[0.30, 1.0)	2+
	[1.0, 5.0)	3+
	>= 5.0	4+

ALT = alanine aminotransferase; AST = aspartate aminotransferase; SI = Le Système International d'Unités (International System of Units).

SAP SCT-MD-60 Allergan

Page 50 of 53

17.0 CHANGES TO ANALYSES SPECIFIED IN PROTOCOL

Only the following changes have been made to the protocol version 3.0: 30 Jun 2020.

Per protocol section 11.3, demographic parameters to be summarized include weight z-score and height z-score. However, these will be listed but not summarized.

No other changes have been made to the analyses specified in the protocol.

Page 51 of 53

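### The SAP's definitions of treatment-emergent and newly emergent adverse events omit the protocol's seriousness criterion, and the SAP does not declare the change

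*SAP*

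**What the plan says.** Protocol 11.6.1.1 gives two routes by which an event already present before dosing becomes a TEAE. It covers an event "that was present before the first dose but increased in severity or seriousness will be considered a TEAE". The protocol's NEAE definition for the down taper uses the same two criteria.

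SAP 10.1 gives one route. Among events already present, it counts as a TEAE only one that "was present before the date of the first dose of double-blind investigational product and increased in severity during the double-blind acute treatment period" or, respectively, the down taper. Its NEAE definition is narrowed in the same way, to an event that "was present before the start of the down-taper period but increased in severity during the down-taper period". Where more than one pre-dose AE shares a preferred term, "the AE with the greatest severity will be used as the benchmark for comparison with the AEs occurring" on treatment; seriousness plays no part.

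SAP 17.0 sets out the departures from protocol version 3.0. The only one listed is that weight and height z-scores will be listed rather than summarized. It then says: "No other changes have been made to the analyses specified in the protocol".

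**The concern.** The SAP removes a criterion from both definitions and at the same time asserts that nothing else has changed. A statistician programming from the SAP would apply a narrower definition than the protocol's, and a reader of SAP 17.0 would not know.

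The events affected are those that turn serious on treatment without a higher severity grade. Safety is part of the primary objective (Protocol 7.1), and TEAE incidence is the first safety endpoint listed in Protocol 11.6. Under the SAP these events would be absent from the TEAE tables by system organ class and preferred term, by severity and by causal relationship, and from the NEAE table. The SAE incidence summary does not replace all of that, because it is specified by period, system organ class, preferred term and arm, without a breakdown by severity or causality.

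**Working it through.** No arithmetic applies. The check compares the two documents and then runs test cases through both rules.

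**Step 1: the definitions side by side**

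| Element | Protocol 11.6.1.1 | SAP 10.1 |
|---|---|---|
| TEAE, event present before first dose | increase in severity or seriousness | increase in severity |
| NEAE, event present before the taper | increase in severity or seriousness | increase in severity |
| Benchmark when several pre-dose AEs share a preferred term | none stated | greatest severity |
| Listed as a change in SAP 17.0 | not applicable | no |

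**Step 2: are the two attributes distinct?** Yes. Protocol 10.1.2.2 grades severity as mild, moderate or severe by interference with everyday activities. Protocol 10.1.2.2.1 defines seriousness by outcome, such as hospitalization or threat to life. The two are recorded as separate items for each AE, so one can change without the other.

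**Step 3: test cases, same preferred term before dosing and on treatment**

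| Before first dose | On treatment | TEAE by protocol | TEAE by SAP |
|---|---|---|---|
| moderate, non-serious | severe, non-serious | yes | yes |
| moderate, non-serious | severe, serious | yes | yes |
| moderate, non-serious | moderate, serious | yes | **no** |
| severe, non-serious | severe, serious | yes | **no** |
| severe, serious | severe, serious | no | no |

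Rows three and four are the disagreement. In row four there is no grade above severe, so under the SAP the event can never qualify, and seriousness is the protocol's only route. Replacing first dose by start of taper gives the same result for NEAEs. The NEAE reference pool is larger, because it includes events that arose during the 8 weeks of treatment.

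**Step 4: does re-recording the event rescue it?** Protocol 10.1.2.2.1 says that if "any nonserious AE worsens and eventually meets the criteria for an SAE, that AE should be recorded as a new SAE". That creates a new record. But SAP 10.1 classifies AEs by preferred term, so a new record with the same term was still present before first dose, and without a higher grade it fails the test.

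**Step 5: can pre-dose events exist?** Yes. AEs are collected from the signing of consent (Protocol 10.1.2.2), and screening may run from Day -21 to Day -1. One concrete route is suicidal ideation. Exclusion 7 covers C-SSRS ideation items 3 to 5 in the past 6 months but not items 1 and 2, although exclusion 8 still removes anyone judged at risk. Protocol 10.1.2.1 requires any positive score to be recorded as an AE or SAE.

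**The case against.** The strongest reply is that no serious event disappears from the report. SAP 10.1 defines an on-therapy SAE by date alone, from first dose to 30 days after last dose. It tabulates SAEs by period and arm and lists every subject with one. TEAE status plays no part. This stands, and it limits the consequence to the TEAE and NEAE tables.

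The SAE and TEAE tables could also disagree under the protocol's own wording, as the last test case shows: it is an on-therapy SAE but not a TEAE by either rule. This stands too. Restoring the criterion narrows the mismatch without removing it.

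The affected set is narrow. It needs the same preferred term before dosing, non-serious then and serious later, with no rise in grade. An event that worsens to the point of hospitalization would often rise in grade as well and so pass the SAP's test. Suicidal ideation and behavior are tabulated from the C-SSRS in any case (SAP 10.5). Safety is analyzed descriptively and both arms follow the same rule. All of this bears on size, and none of it makes the two definitions agree.

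Finally, the protocol has no benchmark rule, so adding seriousness to the SAP's rule might be called a new design choice. It is better seen as a consequence. To apply the protocol's criterion, one has to know whether the pre-dose event was already serious.

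**Conclusion.** The concern holds. Both SAP definitions are wrong as written against the protocol, no other SAP text restores seriousness, and the statement in SAP 17.0 is inaccurate on this point. A pre-dose event that turns serious at an unchanged grade is misclassified.

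The importance is low. The number of events cannot be estimated from the documents and is probably small. SAE reporting still captures them, and no efficacy result or test is affected. What remains is that each misclassified event is serious and that the TEAE and NEAE rates would not follow the protocol's definition. The conclusion rests on the SAP being applied literally and on events being matched by preferred term, as SAP 10.1 states.

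**What to change.** In SAP 10.1, add *or seriousness* after *severity* in both the TEAE and the NEAE definitions. Extend the benchmark rule so that on-treatment events are compared with the greatest pre-dose severity and also with whether any pre-dose event of that preferred term was serious. For NEAEs, make the same comparison with the status before the start of the taper.

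If the narrower definition was intended, SAP 17.0 should declare and justify it instead.

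The cost is a few words in the SAP and a small change to the derivation of the TEAE and NEAE flags. Seriousness is already recorded for each AE (Protocol 10.1.2.2), so nothing new has to be collected. The change should be made before unblinding, so that it cannot appear to depend on the data.
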